10.2. Method of analysis

For the primary clinical outcome, the relative incidence of the primary clinical endpoint will be compared between allele scores 0 versus ≥ 1 and across individual allele scores 0-4 inclusive. Significance will be set at $p<0.05$. For the laboratory measures in a subset of women in hospitals local to WHRI, ex-vivo IL-1Ra functionality in freshly obtained leucocytes will be assessed by flow cytometry and/or protein/gene transcription assays. For these studies, at least 26 samples are required to detect $\geq 25\%$ increase in IL-1Ra levels from control-treated samples for within-subject comparisons ($\alpha=0.05$; $1-\beta=0.9$).

Ethics

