6.5. Study Scheme Diagram

7. Subject population

7.1. *Inclusion criteria*

- ≥18 yr old females of any gestational age,
- Singleton or twin pregnancy,
- requesting an epidural for labour analgesia.

7.2. *Exclusion criteria*

- Unwilling or unable to give consent
- Refusal of consent for competent participants,
- Inability to understand written and/ or verbal English
- immune/genetic syndromes/mutations,
- microbiologically proven infection prior to epidural insertion,
- established pyrexia
- intrauterine death.

8. Study Design

This is an observational mechanistic cohort study in which the development of fever after epidural analgesia and/or antibiotic prescription will be correlated with an allele score generated by the presence/absence of polymorphisms in the IL-1Ra gene. The primary clinical outcome is masked to genomic analyses. 637 women in active labour or commencing induction of labour will be studied. Participants will be selected for the study from antenatal clinics and/or following admission to labour ward. Participants will be informed about the study by their obstetric and/or anaesthetic team. No vulnerable groups will be included. Duration of participation will be from epidural insertion until birth of the baby.

9. Study procedures

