10.1. Sample size

Based on the IL-1Ra Consortium score (Interleukin 1 Genetics, 2015), women with low IL-1Ra secretion associated with an allele score 0 comprise ~12% of the population. We hypothesise that these women are more likely to sustain ERMF or be prescribed antibiotics for >2 temperatures >37.5°C over a two-hour period, compared to women with higher IL-1Ra secretion (allele score ≥ 1). The overall incidence of ERMF in EPIFEVER was 13.4% (probably an underestimate with broader inclusion criteria and lower temperature threshold for antibiotic use, as per RCOG guidelines). If individuals with an allele score 0 are more likely to develop ERMF (~22%), compared with women with IL-1Ra allele scores ≥ 1 , at least 637 women will be

required to detect an absolute difference in primary outcome of ~13%, assuming 9% incidence in women with allele scores ≥ 1 ($\alpha=0.05$; $1-\beta=0.2$).

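### The primary comparison of fever by allele score makes no provision for ancestry, so population structure could bias it; the size cannot be determined from the protocol

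*Protocol*

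**What the plan says.** Section 10.2 of the protocol sets the primary analysis: "the relative incidence of the primary clinical endpoint will be compared between allele scores" 0 and ≥1, and also across the individual scores 0 to 4, at a 5% significance level. No model, covariate or stratification is named.

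Other sections bear on who is compared and what is recorded:

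- **Design (section 8).** An observational cohort in which the exposure is an allele score built from IL-1Ra gene variants.
- **Eligibility (7.1, 7.2).** Entry is open to "≥18 yr old females of any gestational age" with a singleton or twin pregnancy who request an epidural. The nearest thing to a population restriction is a language exclusion.
- **Data (6.4, 9.9, 11.1 Source data).** Temperature, antibiotics, obstetric intervention, delivery, complications and level of care are listed, with medical history and note review in the schedule. Ethnic group is not named.
- **Genotyping (12.5).** Polymorphisms by polymerase chain reaction, with no ancestry markers mentioned.
- **Bias control (8, 9.3).** Masking only.
- **Sample size (10.1).** One external figure is applied to the whole cohort: "women with low IL-1Ra secretion associated with an allele score 0 comprise ~12% of the population".

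**The concern.** Genotype is not randomised across ancestry groups. Allele frequencies can differ between groups, and so can the rate of the endpoint. Because the endpoint in 6.3 includes antibiotic prescription, differences in care as well as in biology can contribute. When both differ, pooling the groups produces an association between score and outcome even if genotype has no effect within any group. When they differ in opposite directions, pooling hides part of a real effect. Masking protects the assessment of outcome and genotype but does nothing about this.

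At stake is the reading of the study's main result. Section 6.1 sets out to show that IL-1Ra variants are associated with fever, and section 5.2 presents this as confirming a link between IL-1Ra and fever. A significant unadjusted contrast would leave population structure as a rival explanation.

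**Working it through.** **Inputs from the protocol.** N = 637; score-0 share about 12%; incidence about 22% (score 0) and 9% (score ≥1); level 0.05, taken as two-sided because sidedness is not stated. The implied overall incidence is 0.12 × 22% + 0.88 × 9% = 10.6%.

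**The plan's own figure.** The protocol gives no figure for confounding. Its sample size of 637 is used here only as the study size. For 22% versus 9%, a 12% share and 80% power, I get 501 (pooled test) or 567 (continuity-corrected), so 637 does not reproduce. That is a separate matter, and nothing below depends on it.

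**Assumed inputs.** Two ancestry groups A and B of equal size, with no genotype effect within either. Score-0 shares are qA and qB, endpoint rates fA and fB. Each scenario in the table is centred on a 12% score-0 share and an overall incidence of about 10.5%, to stay close to the protocol's figures.

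**Bias.** With equal groups and q = (qA + qB)/2, the pooled rates are

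- score 0: p0 = (qA·fA + qB·fB)/(qA + qB)
- score ≥1: p1 = [(1 − qA)·fA + (1 − qB)·fB]/(2 − qA − qB)

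and the difference reduces to

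d = p0 − p1 = (qB − qA)(fB − fA) / [4q(1 − q)].

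So d is zero whenever qA = qB or fA = fB. Both must differ.

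**False-positive rate.** For the pooled two-proportion z test with n0 = 637q and n1 = 637(1 − q), let s0 be the standard error under the pooled rate and s1 the unpooled one. The rejection rate is Φ((d − 1.96·s0)/s1) + Φ((−d − 1.96·s0)/s1).

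Worked for the most extreme row: d = 0.18 × 0.091/(4 × 0.12 × 0.88) = 0.0388; s0 = 0.0375; s1 = 0.0416. The two terms are Φ(−0.83) = 0.20 and Φ(−2.70) = 0.003, about 21% in all.

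| Score-0 share A/B | Endpoint rate A/B | p0 | p1 | d (points) | RR | False positives, formula | Simulated |
|---|---|---|---|---|---|---|---|
| 9% / 15% | 9% / 12% | 10.9% | 10.4% | 0.4 | 1.04 | 5.5% | 5.5% |
| 8% / 16% | 8% / 13% | 11.3% | 10.4% | 0.9 | 1.09 | 6.4% | 6.4% |
| 5% / 19% | 8% / 13.1% | 12.0% | 10.3% | 1.7 | 1.16 | 8.7% | 8.6% |
| 4% / 20% | 7% / 14.1% | 12.9% | 10.2% | 2.7 | 1.26 | 13.2% | 13.1% |
| 3% / 21% | 6% / 15.1% | 14.0% | 10.1% | 3.9 | 1.38 | 20.6% | 20.2% |
| 12% / 12% | 6% / 15.1% | 10.6% | 10.6% | 0 | 1.00 | 5.0% | 4.9% |

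The simulated column uses 200,000 studies of 637 women per row.

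**Opposite direction.** Assume score-0 shares of 5%/20%, endpoint rates of 16%/8% in women with score ≥1, and a true 13-point excess for score 0 in each group. Then p0 = (0.05 × 0.29 + 0.20 × 0.21)/0.25 = 22.6%, and p1 = (0.95 × 0.16 + 0.80 × 0.08)/1.75 = 12.3%. The true 13 points appear as 10.3.

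**The case against.** The strongest reply is that this belongs to the statistical analysis plan. Section 10.2 is one short sentence. It does not rule out covariates, and section 15 has the study committee review a statistical analysis plan that is not shown. The protocol prints no case report form, its data lists cover endpoints more than baseline variables, and medical history or note review (9.9) might capture ethnic group. All of that is fair. That the comparison is unadjusted is inferred from silence about adjustment. The point survives because the protocol states a primary method for an observational genetic association, and nothing in its eligibility, listed data, genotyping or bias control deals with ancestry. Run as written, the comparison is exposed.

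The second reply is that the effect may be negligible. This also stands in part. The mild rows barely move the error rate. Even the most extreme row produces 3.9 points (RR 1.38), against a design difference of 13 points (RR 22/9 = 2.4), so none of these scenarios would by itself produce the planned effect. However, the test declares significance from about 1.96 × 0.0375 = 7.4 points, so a modest bias plus chance can reach it.

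Three stronger readings are tempting, and the protocol does not support them:

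- **That the gap cannot be repaired later.** Samples are linked by a unique number (9.6) and source documents are kept for the archiving period of at least 20 years (11.3), so ethnic group might still be retrieved from the notes.
- **That a significant result could not be attributed to genotype at all.** Bias needs both quantities to differ, and neither is given. The result would be open to another explanation, which is a weaker statement.
- **That the study is underpowered because the score-0 share is really below 12%.** The protocol gives no other share. This would be a separate question resting on invented inputs.

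**Conclusion.** The point holds as a risk to validity, not as a demonstrated error. The primary comparison names no adjustment and the protocol makes no provision for ancestry. The comparison is biased if score-0 frequency and endpoint rate both differ by ancestry, and unbiased in this respect if either is equal.

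The size is unknown. Under assumed inputs with two equal groups, 637 women and no true effect, the false-positive rate runs from about 5.5% to 6.5% for mild differences to about 9% to 21% for large ones. The large rows assume roughly four- to seven-fold differences in score-0 share together with 1.6- to 2.5-fold differences in endpoint rate. Nothing in the protocol says whether such differences exist. The ethnic mix at the recruiting sites is not given either, and should not be presumed. The change is worth making because it is cheap and removes most of an avoidable rival explanation for the main result.

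**What to change.** 1. Add self-reported ethnic group to the electronic case report form, taken from the maternity notes, and name it among the data in 6.4 and 11.1 (Source data).
2. In 10.2, make the primary estimate for score 0 versus ≥1 an odds ratio adjusted for ethnic group by logistic regression, or stratified by it using Mantel-Haenszel. Treat the comparison across scores 0 to 4 in the same way.
3. Report the unadjusted comparison as a sensitivity analysis.
4. Do not adjust for events after epidural insertion, since they may lie on the pathway to fever.
5. Fix a small number of ethnic categories in advance. On the protocol's figures there would be only about 0.12 × 637 = 76 women with score 0 and about 76 × 0.22 + 561 × 0.09 = 67 events in all, so many sparse strata would be unhelpful.

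The cost is one data field and a few degrees of freedom. Self-reported ethnic group captures ancestry only partly, so some residual confounding would remain and should be acknowledged in the report.

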10.3. Annual safety report

This protocol and any subsequent amendments, along with any accompanying material provided to the patient in addition to any advertising material will be submitted by the Investigator to an Independent Research Ethics Committee. Written Approval from the Committee must be obtained and subsequently submitted to the JRMO to obtain Declaration of Sponsorships and approval.

11. Public involvement

The grant funding this work was written in conjunction with The Barts Health patient and public advisory group supporting Barts Research Centre for Women's Health Research Unit- Katie's Team- who have provided views on the study from a mixed group of more than 50 women with varied personal experiences of pregnancy and pregnancy complications, as well as family members, partners and carers attending. To ensure that the full benefit of patient and public involvement in this study, a co-applicant [name] has kindly agreed to be involved in the steering group and provide continuity of advice in partnership with Katie's Team (from whom [name] has kindly agreed to contribute). The design of the protocol has benefited from [name]'s review and [name]'s input into PIS and consent forms. The study will hugely benefit from [name]'s experience in NIHR PPI involvement. Feedback from [name] and Katie's team has helped inform the content and design of patient information sheets, including disseminating information about the proposed study. This has been done in accordance with INVOLVE guidelines on public and patients' engagement.

12. Data management

An electronic CRF will be used to collect data at site level. On data collection times illustrated in section 5, research staff will be responsible for the completion of the electronic CRF throughout the life cycle of the study. The electronic CRF will be hosted on a secure, custom-designed study Queen Mary University of London bespoke clinical study database. The CI will ensure that the study is conducted in compliance with the principles of the Declaration of Helsinki (1996), the principles of GCP and in accordance with all applicable regulatory requirements including but not limited to the Policy Framework and the Medicines for Human Use (Clinical Study) Regulations 2004, and all subsequent amendments, Trust and sponsor policies and procedures and any subsequent amendments. In addition, sponsor auditors and Competent Authority inspectors will be allowed access to CRFs, source documents and other study files to evaluate the study. Audit reports will be kept confidential.

11.1. Source data

Hourly temperature logs kept by midwives as part of routine care for women receiving epidural analgesia. Prescription of antibiotics during labour, obstetric intervention, mode of delivery, complications and level of clinical care required for mother and baby will be recorded from electronic and/or drug charts. Laboratory-based measures of genomic and proteomic signatures associated with developing fever after epidural insertion.

11.2. Confidentiality

The CI has a responsibility to ensure that patient confidentiality is protected and maintained. They must also ensure that participant identities are protected from any unauthorized parties. Information with regards to study patients will be kept confidential and managed in accordance with the GDPR and Data Protection Act 2018, NHS Caldicott Guardian, The Research Governance Framework for Health and Social Care and REC Approval. The PI as well as the study team must adhere to these parameters to ensure that the patient's identity is protected at every stage of their participation within the study. To ensure this is done accordingly, each patient, at time of consent must be allocated a unique screening number by either the PI or a member of the study team before undergoing any screening procedures. The patient's initials (the first letter of their first name and the first letter of their last name)

should be used as a means of linked-anonymizing parameters. This information should be kept on a screening log, which should be updated accordingly throughout the study. Once the patient has completed screening procedures and is enrolled onto the study, the patient will be allocated a randomization number. No identifiable information will be collected from the subjects. The CI is the 'Custodian' of the data and maintains access to the data. No patient identifiable details will be transferred outside the EU. Subjects maintain their right to revoke their authorization for the use of their PID. The patients will be linked anonymised with regards to any future publications relating to this study.

11.3. Record retention and archiving

At the end of the study, as defined by GCP all documentation should be stored by each individual site's archiving facility, for a minimum of 20 years or the maximum period required by the Institution in which the study will be conducted, whichever is longer. The Sponsor should be contacted prior to destruction. A 'close out' visit will be conducted where all study documentation will be prepared for archiving by that site. Records will be retained at each individual site. All records relating to the study should be stored together, including the Investigator Site File (ISF) and CRF. It is the responsibility of the PI to ensure a full set of records is collated and documented. In addition, source documentation should be retained, as per local policy, for the duration of the archiving period.

12. Laboratories

12.1. Central and local laboratories *Error! Bookmark not defined.*

Laboratory samples will be processed in the lab of [name], Translational Medicine & Therapeutics, William Harvey Research Institute, John Vane Science Centre, Queen Mary University of London, [name].

12.2. Sample preparation and collection

After providing informed consent, 20ml of blood will be taken from a cannula inserted as part of routine care for women receiving epidural analgesia. In the unlikely event of blood not being obtained in this manner, lower arm venepuncture will be undertaken by an anaesthetic doctor or nurse trained in phlebotomy and first aid within the research team. This will occur only once. The blood samples will be linked anonymised so that no patient information will be identifiable through the allocation of a unique identification number and processed at the William Harvey Research Institute at [name] by the research team.

12.3. Sample receipt/chain of custody/accountability

Handling of the samples upon arrival at the local and central laboratory will be documented. All samples will be logged upon receipt and the laboratory will ensure that the physical integrity of these samples have not been compromised in transit. If compromise has occurred, the trial coordinating team, as well as the Sponsor, will be informed of this. Upon receipt of samples, laboratory staff will ensure that all samples are accounted for as per the labelling.

12.4. Sample storage and transfer

All blood samples will be pseudo-anonymised. Samples collected at each participating site will be labelled with the participant's corresponding study ID, and kept in a hospital freezer until batched processing. The samples will be routinely collected and transferred to WHRI. The full sample, collection, labelling, logging and transfer procedure will be documented in the study laboratory log. The study coordinating team will provide sites with a Standard Operating Procedure (SOP) on sample collection, processing, and storage. The samples will not be destroyed if a patient withdraws from the study unless they specifically request so. If the patient requests for the samples to be destroyed the Tissue Custodian, (CI) will inform the

lab who will ensure the samples are destructed as per the Human Tissue Act. This will be documented in the TMF and ISF of the participating site

12.5. Laboratory procedures

Single nucleotide polymorphisms will be assessed by polymerase chain reaction. In a subset of women, we will also compare the effect of different local anaesthetic agents on the ability of white blood cells to secrete IL-1Ra using RNA sequencing and flow cytometry.

12.6. End of study

The samples will be used for this study only and will be destroyed according to the Human Tissue Authority's Code of Practice once the final analyses have been performed.

Error! Bookmark not defined.

13. Safety reporting

13.1. *Serious breaches*

The Sponsor of the Clinical Study is responsible for notifying the research ethics committee in writing of any serious breach of the study protocol or the principles of GCP. A 'serious breach', is a breach which is likely to effect to a significant degree:

- The safety or physical or mental integrity of the subjects of the study; or
- The scientific value of the study.

The CI is responsible for reporting any serious breaches to the Sponsor (JRMO) **within 24 hours**. The Sponsor will notify and report to the REC within 7 working days of becoming aware of the serious breach.”

13.2. *General definitions*

An Adverse Event (AE) is any untoward medical occurrence in a subject to whom a medicinal product or procedure has been administered, including occurrences which are not necessarily caused by or related to that product. An AE can therefore be any unfavourable and unintended sign (including an abnormal laboratory finding), symptom or disease temporarily associated with the use of an IMP, whether or not related to the IMP. Only patient discomfort during standing up will be recorded as an AE and assessed accordingly.

13.3. *Study specific adverse events*

There are no adverse events related to this observational study. If venepuncture is necessary (rather than obtaining blood directly from the large bore cannula placed as part of routine care for an epidural), bruising can usually be prevented by applying pressure once the needle/cannula has been removed. Risk of infections from venepuncture for a short time frame are minimal and will be reduced by using sterile techniques (cleaning the area with alcohol, wearing gloves, and covering the insertion point with a plaster once the process is finished). The procedure will be performed by an anaesthetist or trained staff following the WHO guidelines (best practice in phlebotomy, 2010).The risks to participants donating synovial and epithelial tissue during surgery, is the same as the risks of the surgery itself.

14. Monitoring and auditing

14.1. Quality control and quality assurance

The Sponsor or delegate retains the right to audit any study, study site or central facility. In addition, any part of the study may be audited by the funders where applicable. Monitoring will involve a review of the ISF as well as 10% of source data verification. This will involve direct access to patient notes, which will include the review of consent forms and other relevant investigational reports. Missing data will be sought, unless confirmed as not available. A summary of all monitoring activity for this study will be provided to the Sponsor at least every six months. All sites will undergo an on-site site initiation visit. On site monitoring visits will then occur within six months or 10 patients, whichever is sooner as per monitoring plan. At the end of the study all sites will undergo an on-site close out visit.

14.2. Audit and Inspection

This study may be audited by representatives from the coordinating centre and the Sponsor or its delegate. The investigator and institution will be informed of the audit outcome. Investigators are obliged to cooperate in any audit allowing the auditor direct access to all relevant documents and allocate his/her time and the time of his/her staff to the auditor to discuss any findings or issues. An audit may occur at any time during or after completion of the study. Inspections may be carried out by the Competent Authority at any time and the investigator should notify the Sponsor immediately if there are any such plans for an inspection.

15. Study committees

There will be a study committee for this study comprising at least one lay member, an obstetrician and an obstetric anaesthetist not directly involved in the study. The committee will take on the responsibility for:

- ensuring that views of the participants are taken into consideration,
- advising on the trial protocol,
- advising on changes in the protocol based on considerations of feasibility and practicability,
- assist in resolving problems brought to them by the research team
- monitor the progress of the trial and adherence to protocol
- consider new information of relevance from other sources,
- consider and act on the recommendations of sponsor and/or REC,
- review trial reports, statistical analysis plan, protocol papers and papers for publication.

16. Finance and funding

This study is supported by a project grant from the Obstetric Anaesthetists Association, administered by the National Academy of Academic Anaesthesia. There are no participant study payments or travel expenses available for this study.

17. Insurance and indemnity

The insurance that Queen Mary has in place provides cover for the design and management of the study as well as "No Fault Compensation" for participants, which provides an indemnity to participants for negligent and non-negligent harm. [name] (Queen Mary University of London) is the CI. Queen Mary University of London is also sponsoring and insuring the study.

18. Dissemination of research findings

